**IBT to Treat Irritability.** Prior work suggests, but has not established, that irritability may be reduced by training against hostile interpretation bias. Interpretive biases are well-established targets of training programs to treat anxiety and depression, two phenomena with which irritability shares genetic, concurrent, and longitudinal associations. Indeed, irritability and anxiety share similar cognitive biases towards facial expressions signifying social threat. Following prior work in depression, an IBT program was developed to reduce anger and aggression with the presumptive target being hostile interpretation bias. IBT uses face emotions, mixtures of happy and angry expressions, as social stimuli (Figure 1). In two randomized controlled trials, two daily sessions of sham versus active computer-based training shifted participants' judgments of ambiguous facial expressions from "angry" to "happy." Active training was associated with decreased anger in healthy young adults and aggression in youth with conduct problems. In a small, open trial ( $N=14$ ), colleagues and I showed that four daily sessions of IBT was associated with reduced irritability in youths with DMDD. Both trials demonstrated a robust change in interpretation bias as measured by the same face-set stimuli used in training. However, there is no evidence that IBT results in generalized changes of hostile interpretation bias, i.e.

**Figure 1.** An interpretation bias training session. First the balance point is assessed. It is the point on a continuum of happy to angry faces where a person's judgments of them switch from predominantly happy to angry. Training sessions provide feedback on judgments that encourage happy judgments of two ambiguous faces previously judged as angry. Training effects are measured by another balance point assessment.

changes in interpretation bias to other face-set stimuli or other measures of hostile interpretation bias. Still, the effect of the training on symptoms related to hostile interpretation bias is compelling and supports further investigation to determine whether IBT reduces its intended target, hostile interpretation bias (hypothesis 1.2), under the NIMH plan for treatment development (Strategy #3.1).

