## Summary

Prior work strongly suggests an association between irritability and hostile interpretation bias (hypotheses 1.1). Earlier work also suggests IBT may reduce hostile interpretation bias, but only when hostile interpretation bias is measured by the same stimuli used in IBT. This study will assess whether a reduction in hostile interpretation bias generalizes (hypothesis 1.2). Prior work suggests, but has not proven that that irritable youth are slow to learn benign interpretations (hypothesis 2.1) and this is mediated by neural response (hypotheses 2.2 and 2.3).

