For those randomized to out-of-scanner conditions, this visit will occur at the Anschutz Medical Campus Gary Pavilion outpatient psychiatric clinic in a private laboratory room. For those randomized for in-scanner conditions, this visit will occur at the Anschutz Medical Campus Brain Imaging Center (BIC). See COMIRB Application, Section Q, for facilities description. See COMIRB Application, Section J, for MRI safety screening procedures.

At the start of the second visit, adolescents will complete an out-of-scanner interpretation bias assessment on a laptop approximately 3 minutes. Adolescents will then complete an in- or out-of-scanner session of active or sham IBT depending on their allocation (approximately 18 minutes). Immediately after IBT, all adolescents will complete an out-of-scanner interpretation bias assessment presented on a laptop. To assess whether training on the ‘prototypical’ male face-set generalizes to other face-sets, adolescents will complete another interpretation bias assessment designed by [name] and colleagues. It has nearly identical trial structure, but uses four NimStim^63 face-identities that differ in gender and race along the same 15-morph continuum and takes 7.5 minutes to complete. Details of these cognitive tasks and image acquisition are provided below.

At the end of this session, we will give participants a RedCap link and log on instructions. We will ask them to complete an online assessment via RedCap in one week. For those who opt against completing their assessment online, we will give them a packet of assessment measures.

Based on pilot experience at the NIMH, I anticipate the visit length for each out-of-scanner arm to be one hour long and the visit length for each in-scanner arm to be two hours.

*While COVID-19 safety procedures are still in effect on the Anschutz Medical Campus, the following adaptations will be made to Training, Visit 2, Up to Day 7:*

Adolescents and their caregivers will be screened for COVID-19 symptoms the day before their scheduled Visit 2 in accordance with CHCO site standards or BIC standards, depending on randomization.

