The assessment uses “prototypical” male happy or angry expressions. These were created combining twenty males from the Karolinska Directed Emotional Faces set. Thirteen linear morphs between these expressions generated a set of 15 stimuli, or “morphs,” on a continuum from happy (morph 1) to angry (morph 15). All trials consist of a fixation cross (1000ms plus 500-6000ms jitter, mean 1500 ms), morph presentation (150 ms), visual noise mask (250 ms), and response screen with a question mark (until response). Participants respond via keypress with “angry” or “happy.” Each morph of the full set is presented three times in random order. Data from this assessment is used to estimate each participant’s balance point, or the point along the morph continuum where the participant’s judgments change from predominantly happy to angry.

The training is divided into six blocks. Timing and stimulus presentation are the same as in the assessment block except that feedback was provided after each response. Because some will train during fMRI, which does not allow indefinite timing, the response screen timing is 1500 ms plus 500-6000 ms jitter, mean 2000 ms. Feedback will be presented for 1500 ms. Active training is designed to shift the balance point (measured by a pretraining assessment) toward happy judgments of ambiguous faces. Participants receive positive feedback for rating as happy (and negative feedback for rating as angry) two ambiguous morphs nearest to the balance point and had been rated as angry by the participant during the assessment. Patients will receive encouragement to attend for nonresponses, which are anticipated to be rare. Similarly, sham training provided feedback based on the balance point measured at the beginning of each session during the pretraining assessment block. In the case of sham training, the feedback is designed to reinforce, rather than shift, the current balance point. Regardless of what the baseline balance point is, feedback never encourages incongruent judgments of the three extremes on each end of the morph continuum. Both conditions present each morph twice in random order during each training block. There are six training blocks, consisting of 30 trials each lasting 2.7 minutes. In the scanner, each block will begin with an additional 9.2s of fixation for pre-magnetization and end with an additional 12s of fixation to measure BOLD return to baseline.

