Hypothesis 1.2: Active but not sham, IBT will reduce hostile interpretation bias. Mixed-effects linear regression with balance point (interpretation bias) as a dependent variable and training condition (active vs. sham), and time of interpretation bias assessment (pre- or post-training) as independent variables of interest and person as a grouping variable and random effect. Similar models will test for group differences in active or sham IBT on other measures of hostile interpretation bias after training.

Hypothesis 2.1: The rate of learning new associations to ambiguous faces training will be associated with baseline irritability. For those in the active condition, linear regression will test the association between pre-training ARI (irritability) and learning rate to reversal feedback of baseline angry judgments to the two ambiguous morphs.

Hypotheses 2.2 and 2.3: Active, but not sham, IBT will evoke greater neural response in threat-learning systems. For each person, learning will be modeled with regressors coding the “value” or trialwise likelihood that a participant considers the morph to be angry. The amplitude of BOLD %signal change (activity) or amygdala covariance (generalized psychophysiological interaction; connectivity) related to these regressors represents neural response to value. Critically, these regressors represent learning itself where value is changing towards benign judgments in the active training condition to two ambiguous morphs. These will be carried forward to the second level mixed-effects linear models of the effects of morph by pre-training ARI by training condition. A voxel-wise threshold of  $p < .001$ , whole-brain, cluster corrected to  $p < .05$  via permutation testing or Monte Carlo simulation as appropriate, will be used to identify significant associations. A three-way interaction of change in value by morph by training condition will indicate neural areas where learning is influenced by irritability in active but not sham training of reversals of ambiguous morphs. In addition, our *a priori* identification of the likely role of the amygdala, OFC, and ACC justifies follow-up region-of-interest analyses of mean activity or connectivity extracted from these areas with the same omnibus mixed-effects model.

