Exploratory Hypothesis 3.1: Change in irritability after training is associated with change in hostile interpretation bias. We will investigate this relationship with mixed-effects linear models with ARI (irritability), balance-point (interpretation bias), and time of assessment (pre- or post-training) as within-person variables.

Exploratory Hypothesis 3.2: Change in irritability after training is associated with magnitude of neural threat-learning system response. We will investigate this relationship with mixed-effects linear models with ARI (irritability), mean value-associated connectivity or activity in the amygdala, OFC, and ACC, and time of assessment (pre- or post-training) as within-person variables.

As requested by NIMH scientific review, I will conduct two additional, secondary analyses: 1) a mediation analysis of active IBT on change in irritability and 2) a multivariate analysis of the shared and unique effects of irritability, anxiety, and depression on hostile interpretation bias.

Power analysis. For Aim 1, a sample size of 100 achieves 80% power to detect an effect size of the expected association of at least  $r = .25$  between baseline hostile interpretation bias and baseline irritability using Pearson correlation at a one-tailed alpha of .05. Thus, the proposed study will have sufficient power to detect small to medium sized interaction effects. The study is overpowered for detecting expected effects of IBT on hostile interpretation bias which should be large. For Aim 2, a sample size of 100 likewise achieves more than 80% power to detect the expected large association between baseline irritability and learning. For imaging, using a medium effect size of a term in a general linear model ( $R^2 = .15$ ), the required sample for 80% power is 50 individuals ( $p = .05$ ). Our previous study that examined IBT-related changes to face-emotions was medium to large in the orbitofrontal cortex. Thus, the proposed study will have sufficient power to detect small to medium sized interaction effects. Aim 3 is exploratory; this study may estimate effect sizes for future research.

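### Hypothesis 1.2 is said to assess generalisation, but its named pre/post model can be fitted only to the faces used in training, and the untrained-face test is unnamed, unranked and unpowered

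*Combined protocol and SAP*

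**What the plan says.** **Purpose.** The Background (IBT to Treat Irritability) says of earlier work: "Both trials demonstrated a robust change in interpretation bias as measured by the same face-set stimuli used in training". It adds that there is no evidence of carry-over to other face-sets or other measures. The Summary repeats that reductions have been seen, "but only when hostile interpretation bias is measured by the same stimuli used in IBT", and then states: "This study will assess whether a reduction in hostile interpretation bias generalizes (hypothesis 1.2".

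**Named analysis.** Section F, Hypothesis 1.2, specifies "Mixed-effects linear regression with balance point (interpretation bias) as a dependent variable and training condition (active vs. sham", together with "time of interpretation bias assessment (pre- or post-training) as independent variables of interest" and a random effect for person. It does not name the face-set. One further sentence in the same paragraph says that similar models will compare the arms on other measures of hostile interpretation bias after training. It does not say which measures, in what order, or what follows if they disagree with the main model.

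**Measures.** Under Training, Visit 2, a laptop assessment of about 3 minutes is given before and after training. The NimStim task (four identities, 7.5 minutes) is described only after training, with the purpose: "To assess whether training on the ‘prototypical’ male face-set generalizes to other face-sets, adolescents will complete another interpretation bias assessment". The Intent Attributions questionnaire is given only at the online follow-up, because it cannot be repeated within six months.

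**Power.** For the training effect, section F says only: "The study is overpowered for detecting expected effects of IBT on hostile interpretation bias which should be large". No effect size, alpha or power value is attached to that statement.

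**The concern.** The stated question and the named test do not match. The balance point in the H1.2 model comes from the same pictures on which the active arm has just been rewarded for answering happy. The post-test follows immediately after training. A participant who has learned the answers to two pictures, with no wider change in how ambiguous faces are read, would still show a lower hostile bias on this endpoint.

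The sham arm does not remove this. Sham participants see the same faces equally often, so exposure is balanced. But their feedback reinforces the existing balance point, so only the active arm has shifted answers to learn.

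At stake is what the study may say about Aim 1. If H1.2 is reported as supported on the trained-face model alone, the question that the Summary attaches to it stays open. If the trained-face model is positive and the NimStim or Intent Attributions comparison is not, the plan gives no reading of that result in advance.

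**Working it through.** **1. Which face-set can the pre/post model use?**

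| Measure | Before training | After training | Used in training |
|---|---|---|---|
| Prototypical male faces, 15 morphs | yes | yes | yes |
| NimStim, four identities | none described | yes | no |
| Intent Attributions | no | about one week later | no |

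The section on the Interpretation Bias Training Session derives the balance point from the prototypical male set and says of training: "Timing and stimulus presentation are the same as in the assessment block except that feedback was provided after each response". Only the first row has the two time points that the model needs. That the H1.2 endpoint uses training faces is therefore an inference from the schedule, but no other described measure fits. For the other two rows, a similar model reduces to a post-training comparison of arms.

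**2. Feedback on the two target morphs.** Each block shows each morph twice, and there are six blocks: 2 × 6 = 12 feedback trials per morph, 24 for the two. The assessment shows each of the 15 morphs three times.

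**3. How far could learning two answers move the endpoint?** The documents give no estimator for the balance point, so this is an illustration under assumptions. Count the balance point as the expected number of morphs judged happy. Let the chance of an angry judgement be logistic in distance from the balance point, with slope k per morph and the two targets 0.5 and 1.5 morphs above it. If both answers become always happy and nothing else changes, the shift is the sum of the two former angry probabilities:

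- k = 1: 0.62 + 0.82 = 1.44 morphs
- k = 2.5: 0.78 + 0.98 = 1.75 morphs
- Half-complete learning: 0.72 to 0.88 morphs

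The ceiling is 2 morphs, reached only if both targets were always judged angry beforehand and always happy afterwards.

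**4. The plan's own Aim 1 figure.** It is 80% power with N = 100 for r = .25, one-tailed alpha .05. By Fisher z, atanh(.25) × √97 = 0.2554 × 9.849 = 2.516; 2.516 − 1.645 = 0.871; Φ(0.871) = 0.808. The figure reproduces, but it belongs to H1.1. H1.2 has no number to reproduce.

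**5. Power for NimStim, post-training comparison, 50 versus 50, no covariate.** By the normal approximation, d = (z for alpha + z for power) × √(2/50).

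- Two-sided: (1.960 + 0.842) × 0.2 = 0.56
- One-sided: (1.645 + 0.842) × 0.2 = 0.50

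The noncentral t with 98 degrees of freedom gives 0.57 and 0.50. Power by the same t method:

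| d | two-sided .05 | one-sided .05 |
|---|---|---|
| 0.3 | 32% | 44% |
| 0.4 | 51% | 63% |
| 0.5 | 70% | 80% |
| 0.8 | 98% | 99% |

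Both columns are shown because the only alpha stated for Aim 1 is one-tailed, and it is stated for H1.1. If the trained-face effect were d = 0.8 and half of it carried over, d would be 0.4. All values of d are assumptions; the documents give no expected NimStim effect.

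**6. With a NimStim baseline as covariate.** The detectable two-sided d is 0.566 × √(1 − ρ²): 0.49 at ρ = 0.5 and 0.40 at ρ = 0.7. Both correlations are assumed.

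**The case against.** Generalisation is measured, and its analysis sits inside the H1.2 paragraph. The NimStim task was added for exactly this purpose, and the follow-up section plans an active-versus-sham comparison on Intent Attributions. A reader might infer that the plan does not test generalisation at all, but the documents do not support that. The gap is that these measures are neither named nor ranked under H1.2, and nothing is said about what they decide.

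The formal wording of H1.2, in the Specific Aims and in section F, says only that active training reduces the bias, and the Outcome Measures section presents the balance point as a common measure of it. Read alone, hypothesis and model agree; the conflict is with the Background Summary. That is fair, but the Summary cites H1.2 by number, so the plan's own text ties the two together.

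A reader might also infer that a trained-face result would only repeat what is known. It would not. The sham-controlled trials described in the Background gave two daily sessions to healthy young adults and to youth with conduct problems, and the study in youths with disruptive mood dysregulation disorder was open, with N = 14 and four sessions. A sham-controlled, single-session shift in irritable adolescents would be new, which is a good reason to keep the trained-face model.

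Finally, section F claims ample power only for effects expected to be large, and 98% at d = 0.8 bears that out. What remains is that the claim cites the same prior reports whose change was measured on training faces, so it says nothing about untrained ones.

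**Conclusion.** The mismatch holds. The Summary gives H1.2 the generalisation question, while the pre/post model named for it can use only the trained faces. As written, H1.2 could be declared supported through learned feedback on two morphs. That would move the endpoint by at most about 2 of 15 morphs: about 1.4 to 1.8 with complete learning under the assumed slopes, and 0.7 to 0.9 with half. These figures show that the endpoint would register such learning; they do not predict how much will occur.

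For untrained faces, 50 versus 50 gives 80% power at d = 0.57 two-sided or 0.50 one-sided. At d = 0.4, power is 51% or 63%. Whether that is enough cannot be judged from the documents, which give no expected NimStim effect.

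A reader might infer that a positive H1.2 would trigger a go/no-go decision. The section on knowledge to be gained uses that phrase for a future efficacy trial; it sets no decision rule in this study and does not tie one to H1.2.

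**What to change.** **Section F, Hypothesis 1.2.** Name the active-versus-sham difference in post-training NimStim balance point as a required test for the generalisation claim, with the pre-training prototypical-face balance point as covariate. State its alpha and sidedness. Keep the trained-face pre/post model as the test of engagement on trained stimuli. State that a generalised reduction is concluded only if the NimStim comparison supports it, and give Intent Attributions a stated rank.

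**Section F, Power analysis.** Limit the statement of ample power to the trained-face effect. Add the detectable NimStim effect without a covariate: d = 0.57 two-sided or 0.50 one-sided. The covariate may improve on this, but its correlation with the NimStim score is not given.

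**Cost.** Wording, and a less favourable power statement for the generalisation claim. Both the NimStim score and the covariate are already collected.

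**Optional.** Also give the NimStim task, without feedback, before training. A post-only comparison is interpretable because of randomisation, but it cannot show change within an arm, which a claim of reduction in one arm and not the other calls for. The detectable two-sided d would fall to 0.49–0.40 if the pre-post correlation is 0.5–0.7. The cost is 7.5 minutes at Visit 2 and one prior exposure to those faces in both arms.

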#### Randomization

Within 48 hours of Visit 1, Drs. [name] or [name] will determine if any exclusion criteria are met. This time allows Drs. [name] and [name] to consult each other or clarify information with the participants to achieve consensus for any unclear exclusionary diagnosis. If so, [name] will call the participants to thank for their participation, inform them of their exclusion, and cancel their second visit. Some exclusionary criteria are not stable, and it is likely the participants will be eligible during the study period. In that case, participants will still be

marked as a “Screen Failure,” in the consented, but not enrolled, category. However, they will be offered the opportunity to reschedule in the future. In this case, the participants will need to repeat visit 1.

During the pilot phase, eligible adolescents will not be randomized to a study arm, but will be invited to follow procedures for any arm. After pilot, eligible adolescents will be randomized for a 2 x 2 factorial, single blinded, randomized controlled trial, eligible adolescents will be assigned to one of four arms representing TRAINING (active or sham IBT) and SCANNING (in- or out-of-scanner IBT). First, scan ineligible patients will be assigned to out-of-scanner training. Second, randomization will use established minimization procedures (R packages randPack and/or randomizeR) to ensure the four arms are similar in terms of sex, age, socioeconomic status (SES), and IQ. The single blind is required so I may track adolescents with acceptable data. Acceptable behavioral data are at least 70% accuracy on extreme morphs (see [name] et al. for the development of this threshold) and, if applicable, scans of acceptable quality (see below). Allocation to any arm will end when the accrual goal of 25 adolescents with acceptable data have been reached for a total N=100. Since this is a small trial that is not intended to assess clinical efficacy, promoting power and ensuring balance across confounds outweigh the potential for allocation bias due to single-blinding or minimization procedures.

#### Training, Visit 2, Up to Day 7

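### Hypothesis 1.2, generalisation: the untrained-face comparison has no baseline adjustment, and the claim of being overpowered rests on trained-face evidence only

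*Combined protocol and SAP*

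**What the plan says.** The Summary that closes the Background makes generalisation the question of this hypothesis: "This study will assess whether a reduction in hostile interpretation bias generalizes (hypothesis 1.2"). The Background, under IBT to Treat Irritability, explains what that means: "changes in interpretation bias to other face-set stimuli or other measures of hostile interpretation bias". It adds that "there is no evidence that IBT results in generalized changes of hostile interpretation bias". Of the earlier trials it says: "Both trials demonstrated a robust change in interpretation bias as measured by the same face-set stimuli used in training".

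Section F, Hypothesis 1.2, writes out one model: a mixed-effects regression of balance point on training condition and time (pre or post), with person as random effect. It names no face-set. All other bias measures are covered by "Similar models will test for group differences in active or sham IBT on other measures of hostile interpretation bias after training".

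The schedule under Training, Visit 2 opens with one short task: "At the start of the second visit, adolescents will complete an out-of-scanner interpretation bias assessment on a laptop approximately 3 minutes". After training there is a second assessment, and then the NimStim task (four identities, 7.5 minutes), introduced there as the test of generalisation. The online assessment section says outright that the intent-attribution questionnaire can be given only after training.

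Minimisation is meant to "ensure the four arms are similar in terms of sex, age, socioeconomic status (SES), and IQ". The covariate rule in Section F, Hypothesis Testing, adds anxiety, depression, pubertal development and scanner setting. The pre-training balance point is in neither list. The power analysis calls the study overpowered for the effect of IBT on hostile interpretation bias because that effect is expected to be large. It gives no effect size, alpha or detectable difference for this hypothesis.

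**The concern.** The measures that would answer the generalisation question are the ones whose model is not defined. A measure taken once cannot carry a pre/post term, so the written-out model cannot simply be reused. The most obvious prognostic variable, the participant's own bias just before training, is not planned as a covariate, and the existing covariate rule could never bring it in. The score should be complete in both arms, because active and sham feedback are both set from it.

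Separately, the power statement borrows its expected effect from the trained faces. The Summary itself limits that evidence: earlier work suggests an effect "but only when hostile interpretation bias is measured by the same stimuli used in IBT". Transfer to new faces could be much smaller. A reader who takes the study to be overpowered throughout could then read a null NimStim result as proof that training does not generalise, when the comparison may simply have lacked power.

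**Working it through.** **Inputs from the documents.** 50 active and 50 sham (Specific Aim 1). Allocation continues until each of the four arms has 25 participants with acceptable data (Randomization), so 50 vs 50 is the analysed number. The only alpha stated for Aim 1 is one-tailed .05, for the correlation in Hypothesis 1.1.

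**Assumed, because the documents are silent.** Alpha for Hypothesis 1.2 (two-sided .05, with one-sided .05 alongside); the standardised effect d on untrained faces (0.3 to 0.8); the correlation ρ between the pre-training trained-face balance point and the post-training NimStim balance point (0 to .7).

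**Step 1: the plan's own figure.** For r = .25, N = 100, one-tailed .05, the Fisher z calculation is atanh(.25) × √97 − 1.645 = 0.87, which gives 80.8% power. The stated 80% reproduces, but it belongs to Hypothesis 1.1. There is no figure for Hypothesis 1.2 to reproduce.

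**Step 2: unadjusted comparison.** The standard error of the arm difference is √(2/50) = 0.20 SD. By the normal approximation the detectable d at 80% power is (1.960 + 0.842) × 0.20 = 0.56 two-sided and (1.645 + 0.842) × 0.20 = 0.50 one-sided. The noncentral t with 98 degrees of freedom gives 0.566 and 0.501. Power by noncentral t:

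| d on untrained faces | two-sided | one-sided |
|---|---|---|
| 0.3 | 32% | 44% |
| 0.4 | 51% | 63% |
| 0.5 | 70% | 80% |
| 0.8 | 98% | 99% |

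If large means d = 0.8 (an assumption), full transfer leaves ample power, and half transfer (d = 0.4) leaves about an even chance of detection two-sided.

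**Step 3: with one covariate.** The residual SD is multiplied by √(1 − ρ²), and degrees of freedom fall from 98 to 97. The equivalent unadjusted size per arm is 50/(1 − ρ²).

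| ρ | detectable d, two-sided | one-sided | two-sided power at d = 0.4 | at d = 0.5 | equivalent n per arm |
|---|---|---|---|---|---|
| 0 | 0.57 | 0.50 | 51% | 70% | 50 |
| .3 | 0.54 | 0.48 | 55% | 74% | 55 |
| .5 | 0.49 | 0.43 | 63% | 82% | 67 |
| .7 | 0.40 | 0.36 | 79% | 93% | 98 |

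At ρ = .1 and .2 the two-sided detectable d is 0.56 and 0.55.

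**Step 4: simulation.** 20,000 runs, two-sided, d = 0.5, regression on arm and baseline. The mean estimate is 0.50 with and without the covariate, so adjustment removes no bias. At ρ = .3, .5 and .7 the SD of the estimate falls from about .20 to .191, .173 and .142. At ρ = 0, power goes from 69.5% to 69.2%, a cost of 0.3 points.

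**Step 5: chance imbalance.** The arm difference in baseline balance point also has standard error 0.20 SD. A one-standard-error imbalance shifts the unadjusted NimStim difference by ρ × 0.20 = 0.06, 0.10 or 0.14 SD at ρ = .3, .5 or .7. This is part of the unadjusted standard error in Step 2, not a further loss on top of it.

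**The case against.** **The correlation is unknown and may be low.** The baseline rests on 45 trials (15 morphs, three showings) of one composite male face, while NimStim uses four identities of mixed sex and race. At ρ of .3 or less the detectable effect barely moves. This stands, and it limits how much can be claimed. Training could also make the correlation differ between arms. With equal arms and equal outcome SDs, the gain then depends on roughly the average of the two correlations, so adjustment remains sound.

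**Post-only NimStim is an inference.** The plan calls the questionnaire post-only but never says so of NimStim. The order of tasks, and a 7.5-minute task that does not fit a 3-minute slot, point that way. Yet the listed out-of-scanner tasks total about 3 + 18 + 3 + 7.5 = 31.5 minutes (taking 3 for the post-test) of a one-hour visit, so an earlier showing is not excluded. This stands: the plan should state the timing, and if NimStim is also given beforehand its own baseline is the natural adjustment.

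**The text does not say the comparison is unadjusted.** That is literally so; it leaves the model undefined. But no passage names this covariate, and the covariate rule cannot select it.

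**An unadjusted randomised contrast is valid, in a small trial not aimed at efficacy.** Agreed: the case rests on precision alone. Even the absence of bias needs a qualification, because only participants with acceptable data count, and they are selected after randomisation. A baseline covariate does not cure that.

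**Conclusion.** The point holds, as a precision improvement of minor to moderate importance and a correction to the power statement. Without adjustment the untrained-face comparison can detect d = 0.57 two-sided or 0.50 one-sided with 80% power. With the covariate, the two-sided figure is 0.54 to 0.40 over assumed correlations of .3 to .7. The benefit is small if the correlation is low and matters little if a large effect transfers in full.

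The overpowered claim is reasonable for the large trained-face effect the plan expects and has no support in the documents for untrained faces. That part needs no assumed correlation. Confidence is medium, because the NimStim timing is inferred and the correlation, effect sizes and alpha are assumptions.

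**What to change.** 1. State when the NimStim task is given and what alpha and sidedness apply to Hypothesis 1.2.
2. If it is given only after training, specify a linear regression of the post-training NimStim balance point on training condition, with the pre-training trained-face balance point as a prespecified covariate. If NimStim is scored per face identity, use the same covariate in a mixed model with person as random effect. If NimStim is also given before training, use its own baseline instead.
3. Leave other covariates to the existing rule in Section F. Keep the planned active-versus-sham comparison on the intent-attribution questionnaire as the second generalisation measure; the same covariate is optional there.
4. In the power analysis, limit the overpowered statement to the trained faces and give the detectable effect for the untrained-face comparison (50 vs 50, unadjusted, 80% power: d = 0.57 two-sided or 0.50 one-sided).

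The cost is analysis-plan wording and one degree of freedom. No new data, visits or participants are needed, because the pre-training balance point is already required to run the training. In the worst case, zero correlation, about 0.3 points of power are lost at d = 0.5.
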